6.9. Imaging Procedures

Slit-lamp examination, and confocal microscopy (if available) must be performed prior to the impression cytology or superficial keratectomy procedure to document site and size of corneal epithelial changes and to correlate imaging with pathologic findings. The slit-lamp examination must include orbit/lid/adnexa, conjunctiva, sclera, cornea, anterior chamber, iris, lens, and anterior vitreous. Full anterior segment (slit lamp) examination including fluorescein staining of the cornea.

It is recommended that the imaging examination be performed at least 24 hrs prior to the procedure.

Confirmatory anterior segment photography is also recommended, if available. Anterior segment exam includes:, conjunctiva, sclera, cornea, lens and anterior vitreous. If anterior segment photography of the cornea is available, representative images will be collected and stored centrally.

6.10. Concomitant Therapy

Any patient taking concurrent medication that may affect the cornea (i.e. amiodarone, some chloroquines) should not be enrolled.

Concomitant use of ophthalmic medications related to allowable underlying ophthalmic conditions is permitted. Any medication (including over-the-counter prescription medications, vitamins, and/or herbal supplements) that the participant is receiving at the time of enrollment, at time of study procedure, and post procedure must be recorded along with:

- Reason for use;
- Dates of administration including start and end dates;
- Dosage information including dose and frequency.

The Medical Monitor should be contacted if there are any questions regarding concomitant or prior therapy.

7. DISCONTINUATION OF STUDY INTERVENTION AND PARTICIPANT DISCONTINUATION/ WITHDRAWAL

7.1. Participant Discontinuation/Withdrawal from the Study

- A participant may withdraw from the study at any time at his/her own request or may be withdrawn at any time at the discretion of the investigator for safety, behavioral, or compliance reasons. This is expected to be uncommon.
- At the time of discontinuing from the study, if possible, an early discontinuation visit should be conducted, as shown in the SoA (Section 1.3). See SoA for data to be collected at the time of study discontinuation and follow-up and for any further evaluations that need to be completed.
- The participant will be permanently discontinued both from the study intervention and from the study at that time.
- If the participant withdraws consent for disclosure of future information, the sponsor may retain and continue to use any data collected before such a withdrawal of consent.
- If a participant withdraws from the study, he/she may request destruction of any samples taken and not tested, and the investigator must document this in the site study records.

7.2. Lost to Follow-up

A participant will be considered lost to follow-up if he/she repeatedly fails to return for scheduled visits and is unable to be contacted by the study site.

The following actions must be taken if a participant fails to return to the clinic for a required study visit:

- The site must attempt to contact the participant and reschedule the missed visit as soon as possible and counsel the participant on the importance of maintaining the assigned visit schedule and ascertain whether the participant wishes to and/or should continue in the study.
- Before a participant is deemed lost to follow-up, the investigator or designee must make every effort to regain contact with the participant (where possible, [3] telephone calls and, if necessary, a certified letter to the participant's last known mailing address or local equivalent methods). These contact attempts should be documented in the participant's medical record.
- Should the participant continue to be unreachable, he/she will be considered to have withdrawn from the study.

Discontinuation of specific sites or the study as a whole is handled as part of [Appendix 1](#). Discontinuation in this study does not mean the participant has discontinued from the associated treatment protocol.

8. STUDY ASSESSMENTS AND PROCEDURES

A signed, written informed consent form (ICF) must be obtained from the participant prior to any study-specific procedures or assessments being performed. The timing of each assessment is listed in the SoA.

- Study procedures and their timing are summarized in the SoA (Section [1.3](#)).
- Protocol waivers or exemptions are not allowed.
- Immediate safety concerns should be discussed with the sponsor immediately upon occurrence or awareness to determine if the participant should continue or discontinue study intervention.
- Adherence to the study design requirements, including those specified in the SoA, is essential and required for study conduct.
- All screening evaluations must be completed and reviewed to confirm that potential participants meet all eligibility criteria. The investigator will maintain a screening log to record details of all participants screened and to confirm eligibility or record reasons for screening failure, as applicable.
- Procedures conducted as part of the participant's routine clinical management (e.g., blood count) and obtained before signing of ICF may be utilized for screening or baseline purposes provided the procedure met the protocol-specified criteria and was performed within the time frame defined in the SoA.

8.1. Safety Assessments

Planned time points for all safety assessments are provided in the SoA (Section [1.3](#)).

8.1.1. Vital Signs

Vital signs will consist of 1 pulse and 1 blood pressure measurement.

Blood pressure and pulse measurements will be assessed with a completely automated device. Manual techniques will be used only if an automated device is not available.

Blood pressure and pulse measurements should be preceded by at least 5 minutes of rest for the participant in a quiet setting without distractions (e.g., television, cell phones)

8.1.2. Adverse Events (AEs), Serious Adverse Events (SAEs), and Other Safety Reporting

The definitions of AEs and SAEs can be found in [Appendix 2](#).

AEs will be reported by the participant (or, when appropriate, by a caregiver, surrogate, or the participant's legally authorized representative).

The investigator and any qualified designees are responsible for detecting, documenting, and reporting events that meet the definition of an AE or SAE and remain responsible for following up all AEs related to the study intervention.

The methods of recording, evaluating, and assessing causality of AEs and SAEs and the procedures for completing and transmitting SAE reports are provided in [Appendix 2](#) .

8.1.3. Time Period and Frequency for Collecting AE and SAE Information

- All SAEs related to the IC or SK procedure only will be collected from the start of intervention until the last follow-up visit at the time points specified in the SoA. However, any SAEs assessed as related to study participation (e.g., study intervention, protocol-mandated procedures, invasive tests) will be recorded from the time a participant consents to participate in the study.
- AEs related to the IC or SK procedure only will be collected from the start of intervention until the last follow-up visit at the time points specified in the SoA (Section [1.3](#)).
- Medical occurrences that begin before the start of study intervention but after obtaining informed consent will not be collected.
- SAEs related to the IC and SK procedure will be recorded and reported to the sponsor or designee immediately, and under no circumstance should this exceed 24 hours, as indicated in [Appendix 2](#) . The investigator will submit any updated SAE data to the sponsor within 24 hours of it being available.
- Investigators are not obligated to actively seek information on AEs or SAEs after the conclusion of study participation. However, if the investigator learns of any SAE, including a death, at any time after a participant has been discharged from the study, and he/she considers the event to be reasonably related to the study intervention or study participation, the investigator must promptly notify the sponsor.

8.1.4. Method of Detecting AEs and SAEs

Care will be taken not to introduce bias when detecting AEs and/or SAEs. Open-ended and nonleading verbal questioning of the participant is the preferred method to inquire about AE occurrence.

8.1.5. Follow-up of AEs and SAEs

After the initial AE/SAE report, the investigator is required to proactively follow each participant at subsequent visits/contacts. Related SAEs will be followed until the event is resolved, stabilized, or otherwise explained, and the epithelial defect is healed, or the

participant is lost to follow-up (as defined in Section 7.2). Further information on follow-up procedures is given in [Appendix 2](#).

8.1.6. Regulatory Reporting Requirements for SAEs

- Prompt notification by the investigator to the sponsor of an SAE is essential so that legal obligations and ethical responsibilities toward the safety of participants and the safety of a study intervention under clinical investigation are met.
- The sponsor has a legal responsibility to notify both the local regulatory authority and other regulatory agencies about the safety of a study intervention under clinical investigation. The sponsor will comply with country-specific regulatory requirements relating to safety reporting to the regulatory authority, Institutional Review Boards (IRB)/Independent Ethics Committees (IEC), and investigators.
- An investigator who receives an investigator safety report describing an SAE or other specific safety information (e.g., summary or listing of SAEs) from the sponsor will review and then file it along with the Investigator's Brochure (IB) and will notify the IRB/IEC, if appropriate, according to local requirements.
- Investigator safety reports must be prepared for suspected unexpected serious adverse reactions (SUSAR) according to local regulatory requirements and sponsor policy and forwarded to investigators as necessary.

8.1.7. Cardiovascular and Death Events

For any cardiovascular (CV) events detailed in [Appendix 2](#) and all deaths, whether or not they are considered SAEs, specific CV and Death sections of the Case Report Form (CRF) will be required to be completed. These sections include questions regarding CV (including sudden cardiac death) and non-CV death.

The CV CRFs are presented as queries in response to reporting of certain CV MedDRA terms. The CV information should be recorded in the specific CV section of the CRF within 1 week of receipt of a CV Event data query prompting its completion.

The Death CRF is provided immediately after the occurrence or outcome of death is reported. Initial and follow-up reports regarding death must be completed within 1 week of when the death is reported.

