10.2.3. Definition of Cardiovascular Events**Cardiovascular (CV) Events Definition:**

Investigators will be required to fill out the specific CV event page of the CRF for the following AEs and SAEs:

- Myocardial infarction/unstable angina
- Congestive heart failure
- Arrhythmias
- Valvulopathy
- Pulmonary hypertension
- Cerebrovascular events/stroke and transient ischemic attack
- Peripheral arterial thromboembolism
- Deep venous thrombosis/pulmonary embolism
- Revascularization

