17.2. SECONDARY SAFETY ENDPOINTS

17.2.1. ADVERSE EVENTS

Adverse Events (AEs) related to the IC or SK procedure only will be collected from the start of intervention until the last follow-up visit at the time points specified in the schedule of activities (Section 3.2).

All Serious Adverse Events (SAEs) related to the IC or SK procedure only will be collected from the start of intervention until the last follow-up visit at the time points specified in the schedule of activities (Section 3.2). However, any SAEs assessed as related to study participation (e.g., study intervention, protocol-mandated procedures, invasive tests) will be recorded from the time a participant consents to participate in the study.

AEs and SAEs will be presented on the ICSK population and coded using MedDRA version 23.0 or above.

An overall summary table of number of participants within each of the categories described below, will be provided by method of tissue collection (impression cytology/superficial keratectomy) summarizing:

- Participants with at least one AE related to the IC or SK procedure.
- Participants with at least one SAE related to the study participation or to the IC or SK procedure.
- Participants with at least one SAE leading to study discontinuation
- Participants with AE leading to death.

AEs and SAEs will be presented in tables by PT and sorted by decreasing frequencies on total, and broken down by maximum grade. AEs will be graded according to the NCI Common Terminology Criteria of Adverse Events (NCI CTCAE) Version 5.0.

Participants will be counted only once for each PT even if they have multiple records of the same PT. If a participant reports an AE more than once within that PT, the AE with the worst-case grade will be used in the corresponding grade summaries.

Document: \\ieedc-vnasc01\Biosdata\GSKGSK2857916\UZA78766\Biostatistics\Documentation\SAP\UZA78766_214098_SAP_v2.0_12OCT2022.docx

Author: PPD Version Number: 2.0
Version Date: 12OCT2022

Template No.: CS_TP_BS016 Revision 6

Reference: CS_WI_BS005

Effective Date: 02Dec2019

AEs leading to Death are those events which are recorded on the Adverse Events page of the parent study eCRF as at least one of the following criteria:

- AE Term: "Death"
- Outcome: "Death related to adverse event"
- Seriousness: Results in death
- Toxicity grade (CTCAE): Grade 5

[figure not shown]
AEs leading to death will be presented in a by-participant listing on the all-treated population.

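### The protocol requires forms for all deaths and listed CV events but collects only related events, and the SAP counts deaths from a parent-study form some participants may lack

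*Protocol*

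**What the plan says.** Protocol 8.1.7 covers the CV events listed in Appendix 2 and every death: "all deaths, whether or not they are considered SAEs, specific CV and Death sections of the Case Report Form (CRF) will be required". Appendix 2, section 10.2.3, repeats the CV requirement for nine categories: "Investigators will be required to fill out the specific CV event page of the CRF for the following AEs and SAEs".

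The two forms have different triggers, both in 8.1.7. For CV events, "The CV CRFs are presented as queries in response to reporting of certain CV MedDRA terms". For deaths, "The Death CRF is provided immediately after the occurrence or outcome of death is reported".

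Protocol 8.1.3 is narrower. For non-serious and other AEs, "AEs related to the IC or SK procedure only will be collected from the start of intervention until the last follow-up visit". For SAEs, "All SAEs related to the IC or SK procedure only will be collected from the start of intervention until the last follow-up visit", with one extension: "any SAEs assessed as related to study participation (e.g., study intervention, protocol-mandated procedures, invasive tests) will be recorded from the time a participant consents". After discharge, the investigator must notify a death only if it is considered reasonably related.

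SAP 17.2.1 repeats the collection rule of 8.1.3. It then provides a row for AEs leading to death in the overall AE summary (ICSK population) and a by-participant listing (all-treated population). Its definition names the source: "AEs leading to Death are those events which are recorded on the Adverse Events page of the parent study eCRF". SAP section 1 states that the data come from participants in another trial of the sponsor or from patients on commercial prescription.

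**The concern.** The forms are required more widely than the events that would prompt them are collected. A site that applies 8.1.3 strictly has no instruction to report an unrelated stroke or a death from myeloma. A site that applies 8.1.7 strictly would record both. The count of deaths or CV events would then depend partly on which section a site followed.

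This bears on a secondary objective, the safety profile of the two procedures. Under a related-only rule, relationship is judged before anything is recorded. A short all-cause list of deaths and major CV events is what would let a reader check that judgement. Without it, a zero in the death row is ambiguous, most of all for participants treated on prescription, for whom no parent trial may hold the information.

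**Working it through.** The documents state no figure on this point, so there is none to reproduce. The check sets the rules side by side for each type of event during follow-up.

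| Event | Form required (8.1.7, 10.2.3) | Reporting step in 8.1.3 | Does the form open? | SAP output that names it |
|---|---|---|---|---|
| Related CV event | Yes | Yes | Yes, after the CV term is reported | AE/SAE tables |
| Unrelated CV event | Yes, under the AE definition in 10.2.1 | None | No: it needs a reported CV term | None visible |
| Related death | Yes | Yes, as an SAE | Yes | SAE tables; the death row only if also on the parent AE page |
| Unrelated death, parent study exists | Yes | None | Yes, if someone reports the death | Death row and listing, if on the parent AE page |
| Unrelated death, no parent study | Yes | None | Yes, if someone reports the death | None visible |

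1. **CV events.** The AE definition in 10.2.1 applies whatever the relationship to the intervention. An unrelated infarction is therefore an AE, and 10.2.3 asks for the CV page. That page is generated by a query on a reported term, and 8.1.3 does not collect the term. The requirement exists but its trigger cannot fire.

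2. **Deaths.** The trigger is the report of a death, which need not be an AE record. The form can be completed for an unrelated death, but 8.1.3 does not tell the site to report one.

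3. **SAP source.** The death row depends on the parent study's AE page. A participant without a parent study cannot contribute through it. For the others, a progression death counts only if the parent study recorded it as an AE. The parent studies' rules are not in these documents. This protocol's 10.2.1 excludes expected progression of the disease under study from AEs; a similar rule in a parent study would leave such deaths out.

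4. **Scale.** The documents give no risk of death over the study period, so the risk p is an assumption. Expected deaths are n × p, and the chance of at least one is 1 − (1 − p)^n. I use n = 25, the maximum, and n = 5, the number of evaluable SK samples at which enrolment stops.

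| Assumed p | Expected deaths, n = 25 | P(at least one), n = 25 | P(at least one), n = 5 |
|---|---|---|---|
| 1% | 0.25 | 22% | 5% |
| 2% | 0.50 | 40% | 10% |
| 3% | 0.75 | 53% | 14% |
| 5% | 1.25 | 72% | 23% |

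The count at stake is zero to about one death. The collection window is often shorter than the four weeks given in the synopsis. It starts at the procedure; after IC a safety visit is needed only for discomfort or an AE, and after SK the two-week visit is needed only if the defect has not healed. The lower rows of assumed risk may therefore be too high for many participants.

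**The case against.** The phrase in 8.1.7 about SAEs concerns seriousness, not relationship. Section 10.2.3 speaks of AEs and SAEs, which could mean those collected under 8.1.3; on that reading the CV rules agree. This has some force, and the CV conflict does depend on applying the AE definition of 10.2.1 as written. It does not help for deaths, where 8.1.7 covers all of them.

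The related-only rule was also a deliberate amendment, suited to a study of procedure safety. That is fair, and it is why restricting the forms is an acceptable alternative. However, the visible summary of changes lists 8.1.3 and 8.1.5 for this change and not 8.1.7 or 10.2.3.

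A reader might infer four stronger conclusions that the documents do not support:

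- **Unrelated deaths cannot reach the data or tables at all.** Section 8.1.7 itself requires a Death form for every death. SAP 17.2.1 provides a row and a listing through the parent study with no stated relatedness filter, and promises a listing of all secondary safety data. Protocol 9.3 likewise promises that all available safety data will be listed and tabulated.
- **The two rules cannot both be followed.** For deaths they can: a site may record only related AEs and still complete a Death form.
- **A death would appear as a withdrawal or loss to follow-up.** Section 7.2 concerns participants who cannot be contacted, not known deaths, and the SAP disposition section is partly redacted.
- **The 4 deaths among 35 patients in the phase 1 trial (Protocol 2.2) give the expected rate.** No time frame is given for those deaths, so this is not a four-week risk. It shows only that all four were from progression.

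**Conclusion.** The mismatch stands, as a minor point. Unrelated CV events have no collection route, provided 10.2.3 is read with the AE definition. Unrelated deaths have a required form but no matching reporting step in 8.1.3 and no named output in the visible SAP. The only defined source for AEs leading to death is a parent-study form that prescription participants may lack and that may omit progression deaths, so a zero in that row cannot be read as no deaths.

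The practical size is zero to about one death under assumed risks of 1% to 5%, in a descriptive study of at most 25 participants. The primary endpoint, pathology of the corneal sample, is unaffected. The conclusion rests on the visible text; a redacted part of the disposition section or the separate output templates could supply a death category.

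**What to change.** Reconcile Protocol 8.1.3, 8.1.7 and 10.2.3 with SAP 17.2.1.

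Preferred:

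- Add to 8.1.3 that deaths from any cause, and the CV events of 10.2.3, are reported regardless of relationship from the procedure to the last follow-up.
- In SAP 17.2.1, take deaths from this study's own Death and AE forms, supplemented by the parent eCRF where there is one, and state the source for each type of participant.
- List deaths and CV events by participant with date, cause and relationship, apart from the procedure-related AE tables.

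If the sponsor does not want unrelated events, restrict 8.1.7 and 10.2.3 to related events and state in the report that unrelated deaths and CV events were not collected. The SAP source for deaths still needs correcting.

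The preferred option costs a few sentences of protocol and SAP text, one listing from forms that already exist, and a handful of extra records.

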8.2. Biomarkers

Cornea tissue samples will be collected to evaluate the composition of microcyst-like epithelial changes observed in participants treated with belantamab mafodotin. Samples will be collected according to the schedule described in the SoA and, as detailed in the laboratory manual, provided separately to sites.

GSK may store samples for up to 3 years after the end of the study to achieve study objectives. Additionally, with participants' consent, samples may be used for further research by GSK or others such as universities or other companies to contribute to the

understanding of the pathophysiology of belantamab mafodotin-associated keratopathy, the development of related or new treatments, or research methods.

8.3. Data Collection

Minimal additional data will be collected to adequately characterize the development of the corneal epithelial changes in participating patients.

- a. Patient Demographics & Disease characteristics
- b. Limited Medical History and prior cancer treatment
- c. Belantamab mafodotin treatment Exposure
- d. Ocular History including the time of development of keratopathy, and the grade.

9. STATISTICAL CONSIDERATIONS

This is an exploratory study, and only descriptive statistics apply.

Statistical analysis will be done by the sponsor or under the authority of the sponsor. A general description of the statistical methods to be used to analyze the safety data is outlined below.

